12.2.3.3 Regulatory Reporting Requirements for SAEs

The Sponsor or Sponsor representative will report fatal or life-threatening SAEs that are unexpected suspected adverse reactions to the relevant regulatory authorities within 7 calendar days, and non-fatal or life-threatening SAEs that are unexpected suspected adverse reactions within 15 calendar days as Investigational New Drug (IND) Safety Reports, in accordance with 21 CFR 312.32. Prompt notification of SAEs by the Investigator to the appropriate project contact for SAE receipt is essential so that legal obligations and ethical responsibilities towards the safety of other patients are met.

12.2.3.4 Reporting Safety Information to the IRB/IEC

The Investigator, or responsible person according to local requirements, will comply with the applicable local regulatory requirements related to the reporting of SAEs to the Institutional Review Board (IRB)/Independent Ethics Committee (IEC).

All Investigators involved in studies with this drug will receive a copy of each IND Safety Report. When an Investigator receives an IND Safety Report or other safety information (e.g., revised Clinical Investigator's Brochure/Investigator's Brochure), the responsible person according to local requirements is required to promptly notify his or her IRB/IEC.

12.2.4 Follow-up of Adverse Events

The Investigator is required to proactively follow each patient and provide further information regarding AEs and SAEs. All AEs and SAEs will be followed until 30 (+4) days after the last dose of study drug, resolution of the event, until the condition stabilizes, until the event is otherwise explained, or until the patient is lost to follow-up, whichever occurs earlier. Once resolved, the appropriate CRF entries and event reporting forms will be updated, as appropriate.

All AEs and SAEs documented at a previous visit/contact and designated as ongoing will be reviewed at subsequent visits/contacts. The Investigator will ensure that follow-up includes any supplemental investigations as may be indicated to elucidate the nature and/or causality of the AE or SAE. This may include additional laboratory tests or investigations, histopathological examinations, or consultation with other health care professionals.

The Sponsor or the Sponsor's designee may request that the Investigator perform or arrange for the conduct of supplemental measurements and/or evaluations to elucidate as fully as possible the nature and/or causality of the AE or SAE. The Investigator is obligated to assist. If a patient dies during participation in the study or during a recognized follow-up period, the Sponsor will be provided with a copy of any post-mortem findings, including histopathology.

New or updated information will be recorded on the originally completed SAE forms, with all changes signed and dated by the Investigator. This information will also be entered into the CRF.

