Patients will be followed for safety monitoring for 30 (+ 4) days after their final study drug infusion and will have an End of Study visit by telephone at the following times: either (1) at completion of the Extension Phase or (2) at early termination if the patient voluntarily withdraws consent. Patients who terminate the study prematurely will have all ET assessments performed. Patients who terminate the study prematurely who are unable to be on-site for the ET visit will be contacted by telephone for safety follow-up.

If withdrawn from study drug, the patient will continue study visits to the end of Treatment Period 12.

Double-Blind Extension Phase

Patients will enroll in a double-blind extension to begin after the conclusion of Treatment Period 6. Patients in any cohort who have met the stopping rule during the blinded treatment phase will continue study visits in the extension phase without study drug administration. All SEL-212 patients in the extension phase will receive up to an additional 6 monthly doses of SEL-212 at the same dose level as during the Treatment Phase for those that maintain Day 21 sUA <6 mg/dL. Patients who meet the stopping rule during the extension phase will be withdrawn from study drug and will continue study visits to the end of the extension phase.

Data and Safety Monitoring Committee (DSMB)

An independent Data and Safety Monitoring Board (DSMB) will be formed by charter to assist in reviewing safety data and may provide recommendations to the Sponsor regarding study drug dose adjustment or study termination.

Stopping Rules

A patient will be withdrawn from study drug for meeting the following stopping rule:

- sUA level < 2.0 mg/dL, measured 1 hour after the infusion of the second component of study drug is completed during Treatment Period 1
AND
- sUA level > 1.0 mg/dL measured at the Day 21 visit of Treatment Period 1 or sUA level > 6.0 mg/dL at the Day 21 visit of any of Treatment Periods 2-11

Stopping rules will be assessed by an independent, central, unblinded medical monitor.

If withdrawn from study drug during the double-blind treatment period (Treatment Period 1 to 6) or the double-blind extension period (Treatment Period 7 to 12), regardless of reason, the patient will continue study visits to the end of Treatment Period 12. The window for all Day 21 visits is +2/-1 days.

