7.1.3 Follow-Up Phase

Patients will be followed for safety monitoring (30 + 4 days) after their final study drug infusion and will have an End of Study visit by telephone at the following times: either (1) at completion of the Extension Phase or (2) at early termination if the patient voluntarily withdraws consent. Patients who terminate the study prematurely will continue to be followed by having all Early Termination assessments performed. Patients who terminate the study prematurely who are unable to be on-site for the Early Termination visit will be contacted by telephone for safety follow-up.

If withdrawn from study drug, regardless of reason, the patient will continue study visits to the end of Treatment Period 12.

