- Infusion Reactions (an AESI) will be reported to Parexel Safety in the same manner as SAEs using the same form but ticking the AESI box rather than the SAE box.

Adverse events of special interest (AESI) will be recorded specifically for occurrences of: gout flares, infections, malignancies, viral infections, interstitial lung disease, stomatitis, infusion-related reactions including anaphylaxis, thrombosis (e.g., deep venous thrombosis, pulmonary embolism), and the following laboratory tests, if deemed clinically significant by the PI: hyperlipidemia, worsening of renal function tests, proteinuria, and leukopenia.

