1. Phone call at 30 (+4) days after the last study drug infusion for assessment of concomitant medications/procedures, AEs, and SAEs.
2. Visit window at Day 21 of each Treatment Period is +2/-1 days.
3. Assessments at this visit are permitted to be performed remotely (inclusive of collecting applicable lab draws and assessments per protocol visit windows).
4. Study drug dosing to occur 28 days from the previous dose with a window of -4 days to +3 day of the intended dosing day. If a protocol deviation occurs where a patient is not able to be dosed within the dosing day window, for example in the case of COVID-19 restrictions temporarily preventing dosing, the current treatment period will be extended up to a maximum of 90 days without skipping doses for patients with a Day 21 visit sUA value \leq 1.0 mg/dL during Treatment Period 1 or \leq 6.0 mg/dL during Treatment Periods 2-11 in the D21 visit window or subsequent up to the rescheduled dosing visit. Visit window for TP12D28 is -4 to +3 days.
5. Assessment performed at select sites only
6. Full physical exam
7. Directed physical exam
8. Assess vital signs on Day 0 at Time 0 (pre-dose), within + 5 minutes after completion of infusion of the first component of study drug, and 1 hour (+ 5 minutes) after completion of infusion of the second component of study drug.
9. Dispense gout flare medication as needed during the study. Dispense infusion reaction medication at Day 21 of Treatment Periods 1-11.
10. Pretreatment to minimize potential infusion reactions: oral antihistamines at 12 (\pm 2) hours and 2 (\pm 1) hours and IV steroids at 1 (\pm 0.5) hours prior to study drug.
11. Chemistry labs to include: Alkaline phosphatase, alanine aminotransferase (ALT), aspartate aminotransferase (AST), Total Bilirubin, blood urea nitrogen (BUN), Creatinine, UACR, eGFR, Fibrinogen, Glucose (fasting), Electrolytes (sodium, potassium, chloride, bicarbonate, phosphate and magnesium)
12. Hematology labs to include: white blood cells (WBC) count with differential, Red blood cell (RBC) count, Hematocrit (Hct), Hemoglobin (Hgb), Platelet (Plt) count, and absolute neutrophil count (Abneu)
13. Coagulation labs to include: prothrombin time (PT), activated partial thromboplastin time (aPTT), international normalized ratio (INR)
14. Fasting lipid labs to include: total cholesterol, high density lipoprotein (HDL), low density lipoprotein (LDL), triglycerides
15. Collect sample prior to study drug dosing

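### An SAE still unresolved at the end-of-study call has no required further follow-up, because Section 12.2.4 stops at the earliest of five limits, one of them 30 (+4) days after the last dose

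*Protocol*

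**What the plan says.** Protocol Section 12.2.4 sets one rule for non-serious and serious events alike: "All AEs and SAEs will be followed until 30 (+4) days after the last dose of study drug, resolution of the event, until the condition" stabilises, is otherwise explained, "or until the patient is lost to follow-up, whichever occurs earlier".

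The next paragraph of that section says: "All AEs and SAEs documented at a previous visit/contact and designated as ongoing will be reviewed at subsequent visits/contacts".

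Two other provisions determine how these sentences work in practice:

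- The last scheduled contact falls on the same limit. The Synopsis (Follow-Up Phase) says: "Patients will be followed for safety monitoring for 30 (+ 4) days after their final study drug infusion". Footnote 1 of Appendix C describes that contact: "Phone call at 30 (+4) days after the last study drug infusion for assessment of concomitant medications/procedures, AEs, and SAEs". Appendix A carries the same footnote.
- Stopping study drug does not end attendance. Section 7.1.3 says: "If withdrawn from study drug, regardless of reason, the patient will continue study visits to the end of Treatment Period 12". Appendices A and C show AE and SAE collection as continuous over both phases.

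**The concern.** The question here is how long an event already on record is followed, not the window in which new events are collected.

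A list of end-points for follow-up normally lets a serious event run until it resolves or settles. Here a calendar limit is one item in a list in which the earliest item wins, so an SAE can be closed while it is still active, and no sentence in either document exempts it.

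At stake is the final outcome of serious events that start late relative to the last dose. An event that worsens or becomes fatal after the limit need not be captured in that form. Sites may also handle similar events differently, because two adjacent paragraphs can be followed in different ways for a patient who is off drug but still attending.

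**Working it through.** The plan states no figure on this point, so there is none to reproduce. The check is a reading of the text plus date arithmetic.

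**Inputs**

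- Follow-up limit: Day 30 to Day 34 after the last dose (Protocol 12.2.4).
- End-of-study call: Day 30 to Day 34 after the last infusion (Appendices A and C, footnote 1).
- Last on-site visit for a completer: Treatment Period 12 Day 28. Appendix C, footnote 4: "Visit window for TP12D28 is -4 to +3 days". That is Day 24 to Day 31 after the last dose.
- Planned visit span: 12 periods × 28 days = 336 days.

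**Step 1: which limit governs.** Follow-up ends at the minimum of the 30 (+4)-day limit, resolution, stabilisation, other explanation and loss to follow-up. It can therefore never exceed the 30 (+4)-day limit.

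**Step 2: longest follow-up left.** For an event first found k days after the last dose, the most that remains is (30 to 34) − k days.

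| Event first found | Calculation | Longest follow-up |
|---|---|---|
| Day 21 | 30 − 21 to 34 − 21 | 9 to 13 days |
| Day 28 | 30 − 28 to 34 − 28 | 2 to 6 days |
| Day 24 (earliest Day 28 visit) | 30 − 24 to 34 − 24 | 6 to 10 days |
| Day 31 (latest Day 28 visit) | 34 − 31 | at most 3 days |

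The other limits can only shorten these.

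**Step 3: what is required after the limit.**

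- Section 12.2.3.1 does not oblige investigators to look for events in former patients. They notify the sponsor only if they learn of an SAE that they judge reasonably related.
- Section 12.2.4 lets the sponsor request further evaluations and obliges the investigator to assist. The request is optional and aimed at the nature and cause of the event.
- Section 12.2.2.7 requires pregnancy outcomes to be followed after a patient leaves the study. No similar duty exists for an unresolved SAE.

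**Step 4: who is exposed.**

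- *Completers:* the last dose is Treatment Period 12 Day 0, and nothing is scheduled after the call on Day 30 to 34.
- *Patients who leave the study:* there is no later visit at which an ongoing event could be reviewed.
- *Patients off drug who keep attending:* after a last dose at Treatment Period 1 Day 0, the limit falls on Day 30 to 34, but visits run to about Day 336. For 336 − 34 = 302 to 336 − 30 = 306 days, one paragraph of 12.2.4 says follow-up has ended and the next says the event is still reviewed.

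**Step 5: what is lost.** Section 12.2.2.4 allows an unresolved event to be coded at cut-off as not recovered, recovering or unknown, so its status on that date is kept. What is not required is anything later. SAP Section 10.3 plans no table of AE outcome, but it does summarise TEAEs leading to death and TEAEs by maximum intensity. A TEAE that worsens or becomes fatal after the limit need not reach those tables.

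**The case against.** The strongest defence is that the limit looks deliberate. It matches the Follow-Up Phase in Section 7.1.3 and the treatment-emergent window in Section 12.2.1.1, and nothing in the documents requires a longer period. The two paragraphs of 12.2.4 can also be read together, as a formal end to the follow-up duty plus a review at any later visit that happens to exist. Status at cut-off is recorded, and a related SAE or death that the investigator learns of later must still be notified.

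Much of this stands. It makes the point an improvement rather than an error in the results, and it means that attending off-drug patients may well have their outcomes recorded. It does not help completers, who have no later visit, and the joint reading still leaves sites to guess which sentence binds them.

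Three stronger readings are tempting, and the documents do not support them:

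- *Outcomes are lost more often on SEL-212.* A reader might infer this from the stopping rule, and might take the planned 45% response to mean that the other 55% of SEL-212 patients stop early. Non-response in Treatment Period 6 is not early stopping. Placebo patients can also be taken off drug, for an AE, for COVID-19, or under the missing Day 21 sample provision in Section 7.4.1.1. Above all, patients taken off drug keep attending with ongoing events reviewed, so early-stopped patients are better protected than completers.
- *Most follow-up of an early-stopped patient is lost.* The 302 to 306 days above are visit time after the formal limit, not a measure of lost outcomes.
- *Every AESI should be followed without limit.* The list in Section 12.2.1.5 is broad: "gout flares, infections, malignancies, viral infections, interstitial lung disease, stomatitis, infusion-related reactions including anaphylaxis, thrombosis". It begins with gout flares, which Section 10.6.1 expects despite prophylaxis, and it includes infections. Open-ended follow-up of all of these is not clearly cheap.

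**Conclusion.** The point holds as a cheap improvement to safety data. By its wording, Section 12.2.4 releases an unresolved SAE at 30 (+4) days after the last dose, and no other section requires follow-up beyond the end-of-study call or early termination. In size, that is at most 2 to 6 days for an SAE first found at a nominal Day 28 visit after the last dose, and at most 9 to 13 days for one found at Day 21.

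The exposure lies mainly in completers and patients who leave the study. For off-drug patients who keep attending, the issue is a conflict between adjacent paragraphs rather than an established loss.

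The conclusion assumes the literal sense of the earliest-limit clause. The documents do not allow an estimate of how many SAEs would be open at the limit, so no number of lost outcomes is claimed. No efficacy result, sample size or error rate is affected.

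**What to change.** Reword the follow-up sentence in Protocol Section 12.2.4 along these lines:

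> SAEs, and AEs that led to withdrawal of study drug, are followed until resolution, stabilisation, other explanation or loss to follow-up, whichever is first, as far as the patient's consent allows. Other AEs that are still ongoing are followed to the later of 30 (+4) days after the last dose and the patient's last study visit.

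The first sentence removes the 30-day limit where the outcome matters most. The second reconciles the rule with the following paragraph for patients who stay in the study off drug. The SAP needs no change.

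The cost is an amendment to one sentence and a few contacts after the end-of-study call for patients with unresolved serious events or events that ended treatment. The gain is limited for patients who leave the study: loss to follow-up still ends the duty, and after withdrawal of consent only what the patient permits can be collected.

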13. STATISTICS

Details of the statistical methods outlined in the protocol for this study, including the hierarchical ordering of the secondary endpoints, will be documented in a Statistical Analysis Plan (SAP), which will be finalized prior to database lock. The SAP may add additional exploratory analyses; modifications to the planned analyses will be identified as such in the final SAP.

13.1 Sample Size Determination

The primary efficacy criterion in this study is defined as the percentage of the patients who achieve and maintain reduction of sUA < 6 mg/dL for at least 80% of the time during Treatment Period 6 by Day 28.

The sample size estimation is based on the main estimand for the primary efficacy criterion from version 5.0 of the protocol. This estimand considered all patients who discontinue study treatment due to lack of efficacy (e.g., meeting stopping rule), due to treatment-related or non-treatment related AE as treatment failures, as well as initiating prohibited medication that lowers sUA, withdrawal of consent or lost to follow up for reasons other than COVID-19.

Based on the results in the Phase 2 study (SEL-212/201) with SEL-212, the responder rate in all randomized and dosed patients is assumed to be 45% in SEL-212. For placebo, a responder rate of 5% is assumed. Considering a randomization ratio of 1:1:1 for SEL-212A and SEL-212B against placebo, a statistical power of 90%, a two-sided alpha-level of 2.5% and using the Chi-square test with continuity correction for the 2 pairwise comparisons of each SEL-212 dose group against placebo, 32:32:32 randomized and dosed patients will be required for each treatment group. Considering the potential that some randomized patients will terminate the study early (approx. 8%), the number of the patients required to be randomized and dosed in total is 105 (i.e., 35:35:35) to demonstrate efficacy.

Randomized but not treated subjects will be replaced. For the sample size estimation, the Chi-square test is used instead of the Mantel-Haenszel test, although the randomization will be stratified for tophus presence (yes/no), as there is no valid assumption of the distribution of this stratification variable within the eligible patient population.

From an amendment in version 6.0 of the protocol, the main estimand for the primary efficacy criterion was updated to include patients who present a positive COVID-19 test along with severe or critical symptoms of COVID-19, and patients who missed all assessments of sUA during Treatment Period 6, as treatment failures. As these are expected to be unrelated to the treatment then assuming that the number of additional treatment failures to each arm would be roughly equal, the difference in response rates can still be assumed to be 40%, unless the treatment failure rate due to positive COVID-19 tests along with severe or critical symptoms of COVID-19 is sufficiently high that a difference of 40% cannot be observed (I.e. the treatment failure rate in the active arms is >60%, so even if the responder rate for the placebo group is 0%, a difference of 40% cannot be observed).

To mitigate this risk, an additional 15 patients have been added to the study sample size to account for potential treatment discontinuations that may occur due to the ongoing COVID-19 pandemic as a result of the emergence of COVID-19 variants which were not accounted for in the sample size calculations

resulting in approximately 120 patients (i.e., 40:40:40) to be randomized and dosed to demonstrate efficacy.

Sample size calculations were performed with the software package nQuery 8, Version 8.5.0.0.

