attended assessments are less than 7 actual days apart, then the response evaluation of Treatment Period 6 will be missing. Otherwise, the response evaluation will be derived from the available data points.

The proportion of time that the sUA level is < 6 mg/dL, i.e., percentage of non-hyperuricemic time, will be computed by taking the ratio between the time during which the sUA level remains < 6 mg/dL (if necessary, using the linear interpolation method) and the entire time interval within Treatment Period 6 by Day 28 (or last available assessment prior to Day 28 if no assessments are available from Day 28 up to, and including Day 0, pre-treatment (0 h) in Treatment Period 7).

For a patient who has completed Treatment Period 6 to be considered a responder, the proportion of time that the sUA level is < 6 mg/dL (i.e., percentage of nonhyperuricemic time) during Treatment Period 6 by Day 28 must be at least 80%.

Frequency table of the percentage of responder in Treatment Period 6 (patients who achieve and maintain reduction of sUA < 6 mg/dL for at least 80% of the time in Treatment Period 6) will be provided by treatment group. Additionally, a summary table with the total time a patient has sUA values < 6 mg/dL in Treatment Period 6 will be provided by treatment group.

Summary table of the actual values and change from baseline for sUA results will be provided for each scheduled sampling time point by treatment group.

Additionally, mean sUA level, reduction in mean sUA and percent reduction in mean sUA from baseline during Treatment Period 6 will be presented by treatment group.

- Mean sUA level is defined as the area under the sUA time curve (computed using the linear trapezoidal rule during Treatment Period 6) divided by the corresponding time interval.
- Reduction in mean sUA is computed by subtracting baseline sUA level from mean sUA during Treatment Period 6.
- Percent reduction in the mean sUA from baseline is computed as the mean sUA level during Treatment Period 6 minus baseline sUA level divided by baseline sUA level multiplied by 100%.

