### **3.5. Determination of Sample Size**

The sample size estimation is performed for the main estimand for the primary efficacy endpoint from V5.0 of the protocol 'percentage of patients who achieve and maintain reduction of sUA < 6 mg/dL for at least 80% of the time during Treatment Period 6 by Day 28' which defined in Section [6.1](#). This estimand considered the following as treatment failures: patients who discontinue study treatment due to lack of efficacy (eg, meeting stopping rule), patients who discontinue study treatment due to treatment-related or non-treatment related AEs, patients who take prohibited medication that lowers sUA, or patients who are lost to follow up or withdraw consent for reasons other than COVID-19.

Based on the Phase 2 (protocol SEL-212/201) results with SEL-212, the responder rate in all randomized and dosed patients is assumed to be 45% in SEL-212. For placebo a responder rate of 5% is assumed. Considering a randomization ratio of 1:1:1 for SEL-212A and SEL-212B against placebo, a statistical power of 90%, a two-sided alpha-level of 2.5% and using the Chi-square test with continuity correction for the 2 pairwise comparisons of each SEL-212 dose group against placebo, 32:32:32 randomized and dosed patients will be required for each treatment group. Considering the potential that some randomized patients will terminate the study early (approx. 8%), the number of the patients required to be randomized and treated in total is 105 (i.e., 35:35:35) to demonstrate efficacy. Randomized but not treated subjects will be replaced. For the sample size estimation, Chi-square test is used instead of the Mantel-Haenszel test, although the randomization will be stratified for tophus presence (yes/no), as there is no valid assumption of the distribution of this stratification variable within the eligible patient population.

From an amendment in version 6.0 of the protocol, the main estimand for the primary efficacy criterion was updated to include patients who present a positive COVID-19 test along with severe or critical symptoms of COVID-19, and patients who missed all assessments of sUA during TP6, as treatment failures. As these are expected to be unrelated to the treatment, then assuming that the number of additional treatment failures to each arm would be roughly equal, the difference in response rates can still be assumed to be 40%, unless the treatment failure rate due to positive COVID-19 tests along with

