This document is confidential.

severe or critical symptoms of COVID-19 is sufficiently high that a difference of 40% cannot be observed (i.e. the treatment failure rate in the active arms is >60%, so even if the responder rate for the placebo group is 0%, a difference of 40% cannot be observed).

To mitigate this risk, an additional 15 patients have been added to the study sample size to account for potential treatment discontinuations that may occur due to the ongoing COVID-19 pandemic as a result of the emergence of COVID-19 variants which were not accounted for in the sample size calculations resulting in approximately 120 patients (i.e., 40:40:40) to be randomized and dosed to demonstrate efficacy.

Sample size calculations were performed with the software package nQuery 8, Version 8.5.0.0.

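### The sample-size text counts patients with no Treatment Period 6 sUA as failures while the analysis text imputes missing response, and the claim that the difference stays at 40 points does not hold in general

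*Protocol*

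**What the plan says.** **Patients with no Treatment Period 6 (TP6) sUA.** Protocol 13.1 says the version 6.0 amendment added two groups of failures to the main estimand: patients with a positive test and severe or critical COVID-19, and "patients who missed all assessments of sUA during Treatment Period 6, as treatment failures". SAP 3.5 repeats this: "patients who missed all assessments of sUA during TP6, as treatment failures". SAP 6.1, directly below the event list for the main estimand, calls the same patients non-responders and says the unchanged sample size is justified for the modified estimand.

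The event lists do not contain this event. The Protocol synopsis (Primary Efficacy Endpoint and Primary Efficacy Analysis), Protocol 13.4.1 and SAP 6.1 name as composite failures the stopping rule or lack of efficacy, stopping for an adverse event, severe or critical COVID-19, death, and sUA-lowering prohibited medication. All other intercurrent events go to treatment policy.

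Protocol 13.4.1 says that with two or fewer assessments, and the first and last attended less than 7 days apart, "then the response evaluation of Treatment Period 6 will be missing". SAP 9.1 has the same rule. The synopsis and SAP 9.2 multiply impute missing response. SAP 9.2 uses a logistic model with tophus status and treatment. Neither makes an exception for a patient with no TP6 sample.

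**Planning difference.** Protocol 13.1 expects the added failures to be unrelated to treatment. "assuming that the number of additional treatment failures to each arm would be roughly equal", it concludes that "the difference in response rates can still be assumed to be 40" percentage points. The stated exception is that "the treatment failure rate in the active arms is >60" percent, and SAP 3.5 adds the reason: "so even if the responder rate for the placebo group is 0%, a difference of 40% cannot be observed". Protocol 13.1 also records that the version 5.0 estimand, on which the 45% and 5% rates rest, counted "withdrawal of consent or lost to follow up for reasons other than COVID-19" as failure.

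**The concern.** Two things in the sample-size justification do not fit the rest of the plan.

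First, a patient with no TP6 sUA and no listed composite event is a failure under one set of sections and an imputed value under another. The typical case is withdrawal of consent or loss to follow-up. This concerns the confirmatory estimand, and SAP 6.1 contains both versions: an event list without the event, and a paragraph that justifies the sample size with it. If the conflict is still open at unblinding, the handling of these patients becomes a choice made with results in view.

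Second, an extra failure lowers an arm's response rate only if that patient would otherwise have responded. Equal numbers of extra failures are therefore not equal losses of responders when the arms start at 45% and 5%. If the argument fails, the planning difference carried forward to the enlarged trial is not supported by the reasoning given for it.

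**Working it through.** **Inputs.** From Protocol 13.1: 45% versus 5%, two-sided alpha 0.025 per comparison, 90% power, continuity-corrected chi-square, 8% early termination, then 15 patients added to give 40 per arm. The fraction f of extra failures is not given and is treated as an assumption over a range.

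**The plan's own figures.** With mean rate 0.25, d = 0.40, z = 2.241 and 1.282:

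- Uncorrected: n' = [2.241 x sqrt(2 x 0.25 x 0.75) + 1.282 x sqrt(0.45 x 0.55 + 0.05 x 0.95)]² / 0.40² = 26.7.
- Corrected: n = (n'/4) x [1 + sqrt(1 + 4/(n'd))]² = 31.5, so 32 per arm.
- Early termination: 32/0.92 = 34.8, so 35 per arm and 105 in total.

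The stated 32, 35 and 105 all reproduce.

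**Rule for no TP6 sUA.** Suppose k of 40 per arm have no TP6 sUA and no composite event (an assumption).

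| k | 45%/5% already count them as failures, analysis imputes: 40/(1-k/40) | 45%/5% are the imputed rates, analysis counts them as failures: 40 x (1-k/40) |
|---|---|---|
| 1 | 41.0 points | 39 points |
| 2 | 42.1 | 38 |
| 3 | 43.2 | 37 |
| 4 | 44.4 | 36 |

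The rules give different answers, and the direction depends on what the planning rates already contain.

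**When 40 points is kept.** If each arm loses the same number of would-be responders, x points, then (45-x) - (5-x) = 40. Placebo has only 5 points to lose, so x cannot exceed 5. At x = 5 the rates are 40% and 0%, which is where the 60% failure limit comes from. It means losing 5/45 = 11.1% of SEL-212 responders but 5/5 = 100% of placebo responders.

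**When failures are independent of response.** A fraction f in each arm gives 45%(1-f) versus 5%(1-f), a difference of 40 x (1-f) points. With f = 10%, 4 of 40 per arm fail: 4 x 0.45 = 1.8 expected responders are lost on SEL-212 and 4 x 0.05 = 0.2 on placebo. At the text's 60% limit, 45%(1-f) = 40% gives f = 1/9 = 11.1%, placebo 4.4% and a difference of 35.6 points.

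**Power at 40 per arm.** The corrected formula is inverted with n' = n x (1 - 1/(nd))², and power is then read from the uncorrected formula.

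| f | Difference (points) | Power |
|---|---|---|
| 0 | 40.0 | 96.7% |
| 5% | 38.0 | 95.2% |
| 10% | 36.0 | 93.2% |
| 11.1% | 35.6 | 92.7% |
| 16% | 33.6 | 90.1% |
| 20% | 32.0 | 87.6% |

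The largest f that keeps 90% power is 16.2% by this formula and 21.6% by exact enumeration of the same test.

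**The case against.** **The failure wording is history.** Protocol 13.1 and SAP 3.5 narrate a version 6.0 amendment, and the Protocol is now version 6.1. This explains how the wording may have survived. It does not remove the conflict, because these are current sample-size and estimand sections, and SAP 6.1 uses the rule in the present to justify the sample size.

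**The two rules may cover different patients.** The missing-response rule refers to the first and last attended assessments, which do not exist for a patient with no sample. No sample means failure, too few samples means missing, is therefore a possible reading. This stands to the extent that the documents do not settle which rule is meant. But no composite list carries the event, and the imputation text has no exception.

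**Sensitivity analyses cover it.** In the tipping-point grid of SAP 9.2, the cell with response probability 0.01 in both arms nearly reproduces counting missing as failure. It shows how much the choice matters, but it does not say which rule is primary. The third estimand in SAP 6.1 applies the composite strategy only to the listed events, so it does not settle the question either.

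**The 40 points is a declared assumption.** Read as equal net losses of responders, the subtraction is exact and the 60% limit follows from it. That is fair: the fault is a weak assumption rather than a slip of subtraction. But failures described as unrelated to treatment are more plausibly unrelated to response as well. Equal responder loss would require placebo to lose every responder at the limit.

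**Conclusion.** Minor, and wrong as written on both counts. The sample-size text and SAP 6.1 state a rule for patients with no TP6 sUA that the event lists omit and that conflicts with the imputation text. The 40-point argument holds only for equal losses of would-be responders, up to 5 points. Under failure independent of response, the difference is 40 x (1-f). That model, the value of f and the values of k are assumptions; the documents give none of them.

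A reader might go further in four ways that the documents do not support:

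- *The trial is underpowered.* Not shown. The added patients were meant for this risk, and 40 per arm keeps 90% power up to f of about 16% (formula) or 22% (exact).
- *40 points is too high.* Not shown. Version 5.0 counted non-COVID withdrawal and loss to follow-up as failures; the current lists do not. If those patients were the plan's 8% early terminators and are now imputed, the difference would rise to 40/0.92 = 43.5 points. If patients with no TP6 sUA are imputed, only severe or critical COVID-19 remains of the two added failure types. The net direction is uncertain.
- *A further 8% should come off the 40 per arm before applying f.* The ITT set keeps all dosed patients, missing response is imputed, and the 45% rate is stated for all randomized and dosed patients. That deduction risks counting the same loss twice.
- *SAP section 12 should have declared the difference.* That section lists departures from the Protocol. Here the two documents agree with each other, and the conflict lies inside each.

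**What to change.** Change wording only, before unblinding.

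1. Delete the statement that missing all TP6 sUA is a failure or non-response from Protocol 13.1, SAP 3.5 and SAP 6.1, so that they match the event lists and SAP 9.2. State in Protocol 13.4.1 and SAP 9.1 that a patient with no TP6 sUA has a missing response. If failure is what is intended, instead add the event to every composite list (both synopsis passages, Protocol 13.4.1, the tophi-subset responder estimand in Protocol 13.4.2, and SAP 6.1), and limit imputation to patients with some but insufficient TP6 data.

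2. In Protocol 13.1 and SAP 3.5, replace the 40-point statement and the 60% limit with:

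> If a further fraction f of each arm fails for reasons unrelated to treatment and response, and not already counted in the 45% and 5% rates, the expected difference is 40 x (1-f) points; with 40 patients per arm, power stays at or above 90% for f up to about 16% by the planning formula (about 22% by exact enumeration).

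The cost is a few sentences in each document and a slightly less favourable stated planning difference. No patients, visits or analyses are added.
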